## **5.6 Post-study therapy**

The leukemia treatment after the end of the study (defined for different phases see [section 3.7](#)) will be left to the discretion of the investigator and / or the primary physician and the subjects will be treated according to standard of care (e.g. consolidation therapy or allogeneic SCT).

## **5.7 Pregnancies**

The investigator must report to the sponsor any pregnancy occurring in a study subject, or in his partner, during the subject's participation in this study until 28 days after last administration of the study drug. The report should be submitted within the same timelines as an SAE, although a pregnancy per se is not considered an SAE. For a study subject, the outcome of the pregnancy should be followed-up carefully, and any abnormal outcome of the mother or the child should be reported. For the pregnancy of a study subject's partner, all efforts should be made to obtain similar information on course and outcome, subject to the partner's consent. For all reports, the forms provided are to be used.

## 6 Study procedures

### 6.1 Study flowcharts and visit schedules

Table 9: Visit schedule Escalation and Expansion part

	V0 – Screening	Enrolment	V1	V2	V3	V4	V5	V6	V7	V8 – Remission Assessment i	Premature EOS	Post-study Follow-up k
Study – Day	-14 to -1	1 (predose)	1	2-6 daily	7	9	11	18	22	28-45 (all patients)	7-14 days after last dose for safety	Every 3 months
Informed Consent	x											
Check Inclusion/Exclusion Criteria		x										
Demographics, Medical/Treatment History	x											
Physical exam, ECOG, Vital Signs l	x		x		x			x		x	x	
body weight and height m	x		x							x	x	
Full Blood Count a	x		x	x	x	x	x	x	x	x	x	
Chemistry and Coagulation b,c	x		x		x	x	x	x	x	x	x	
TLS chemistry tests d			x	x								
Bone marrow assessment e	x							x f		x	x if progress	
Material shipment for central Review g	x							x		x	x if progress	
HIV-Test	x											
Virus diagnostics n	x											
β-HCG pregnancy test h	x											
ancillary research material o	x									x	x if progress	
Adverse Events			Continuously starting from day 1 until 28 days after last dose of venetoclax									
Concomitant Medication			Continuously starting from day 1 until 28 days after last dose of venetoclax									
Disease status & Survival												x

- a Blood count (hemoglobin, hematocrit, white blood cells, platelets) incl. differential - for screening and remission assessment microscopic differential is required for peripheral blasts. In addition, blood count should be done 3x/week until hematologic recovery and as often as necessary in the opinion of the treating physician
- b Determination of: sodium, potassium, calcium, creatinine, urea, ALAT (GPT), ASAT (GOT), LDH, alkaline phosphatase, bilirubin, total protein, albumin, uric acid, INR, aPTT, fibrinogen.
- c All subjects must receive tumor lysis prophylaxis prior to and during treatment, including chemistries at 24, 48 and 72 hours after administration of the designated cohort dose. For details on tumor lysis prophylaxis and management, refer to section [5.4.5](#) Management of Tumor Lysis Syndrome (TLS) and [Appendix 2](#) – Recommendations for Initial Management of Electrolyte Imbalances and Prevention of Tumor Lysis Syndrome (TLS) for further information. Subjects in the expansion stage only require TLS prophylaxis and management 24, 48, and 72 hours after administration of the designated cohort dose, if clinically necessary.
- d TLS chemistry tests (calcium, inorganic phosphorus, potassium, uric acid, creatinine) on each day of new dose of venetoclax at pre-dose, 6-8 hours and 24 ( $\pm$  2) hours post-dose (see section [5.4.5](#))
- e local bone marrow assessment: cytomorphology including cytochemistry, immunophenotyping, cytogenetics, molecular diagnostics
- f day 18: only BM-assessment for cytomorphology incl. cytochemistry
- g samples for central diagnostics (Hema Lab Dresden): 5 bone marrow and 2 peripheral blood smear slides for cytomorphology and 10ml heparinized bone marrow for immunophenotyping
- h Women of childbearing potential must have a negative serum pregnancy test performed **within 7 days** before first dose of venetoclax
- i Remission Assessment-visit on day 28-45 is required for all patients regardless a subject has prematurely terminated the study treatment for any reason or not (except for death or withdrawn ICF).
- k All patients will be followed-up after last study visit for survival, remission status, further AML therapies (regimes and start dates) and second primary malignancies for minimum 24 months, either by phone calls or visits.
- l vital signs: blood pressure, heart frequency and temperature
- m height only at Screening
- n Virus diagnostics (according to clinical standards): HBs-antigen, HBs-antibody (if positive HBs-antibody – HBV DNA required), anti-HBc, anti-HCV IgG (if positive anti-HCV IgG – HCV RNA required)
- o ancillary research: collection of 9 ml peripheral blood (pB) in EDTA-tube and 5 ml bone marrow (BM) in EDTA-tube + 3 ml heparinized BM at screening, remission assessment and in case of progress (see section [6.5](#))

Table 10: Visit schedule maintenance therapy

Cycle day	Maintenance pre-visit (only done, if V8 of previous treatment phase >14 days)	Eligibility	Cycle 1		End of Cycle 2, 4, 6, 9	End of Cycle 12 = EOS or at Premature EOS f	Post-study Follow-up g
		day -7 to -1	d1	d15	d28 (+/-5days)	d28 (+/-5days)	every 3 months
Physical exam, ECOG	x		x	x	x	x	
Vital Signs, body weight h	x		x	x	x	x	
Full Blood Count a	x		x	x	x	x	
Chemistry and Coagulation b	x		x	x	x	x	
β-HCG pregnancy test		x					
Bone marrow assessment c,d	x				x	x	
Material for central Review e	x				x	x	
ancillary research material i					x	x	
Concomitant Medication	x		continuous till day 28 after last dose of IMP				
Adverse Events	x		continuous till day 28 after last dose of IMP				
Disease status & Survival							x

a Blood count (hemoglobin, hematocrit, white blood cells, platelets) incl. microscopic differential except C1D15. In addition, these evaluations should be done as often as necessary in the opinion of the treating physician

b Determination of: sodium, potassium, calcium, creatinine, urea, ALAT (GPT), ASAT (GOT), LDH, alkaline phosphatase, bilirubin, total protein, albumin, uric acid, INR, aPTT, fibrinogen.

c local bone marrow assessment: cytomorphology including cytochemistry, immunophenotyping, cytogenetics, molecular diagnostics

d Bone marrow assessment and peripheral complete blood count proving a CR/CRp (not CRi) is a prerequisite for the start of maintenance treatment. If CR/CRp is proven at the V8 and maintenance starts within 2 weeks after bone marrow assessment, no additional bone marrow is necessary.

e samples for central diagnostics (Hema Lab Dresden): 5 bone marrow and 2 peripheral blood smear slides for cytomorphology and 10 ml heparinized bone marrow for immunophenotyping

f If a subject discontinues the study for any reason (except for death or loss to follow-up), a premature end-of-study evaluation will be performed 7 to 14 days after the last dose of study drug.

g All patients will be followed-up after last study visit for survival, remission status, further AML therapies (regimes and start dates) and second primary malignancies for minimum 24 months, either by phone calls or visits

h vital signs: blood pressure, heart frequency and temperature

i ancillary research: collection of 9 ml peripheral blood (pB) in EDTA-tube at end of cycle 2, 6 and 12; in case of relapse 9 ml pB and 5 ml bone marrow (BM) in EDTA-tube + 3 ml heparinized BM (see section [6.5](#))

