### 3.4 Leukemia response evaluation and treatment continuation

Early response assessment by bone marrow aspiration will be performed in the time between day 18-21 (only cytomorphology), remission control on day 28-45 (earliest on day 28 and latest on day 45 depending on regeneration of blood counts) counting from day 1 of venetoclax (indicated in the visit schedule in [section 6.1](#)/Table 9).

Patients in CR/CRp ( $ANC \geq 1 \times 10^9/L$ ) may receive venetoclax maintenance treatment at a maximum dose of 400 mg QD p.o. continuously for up to twelve 28-day cycles, if they do not have any other post-remission treatment option (e.g. allo/auto-TX, consolidation chemotherapy etc.). Assessments for safety and efficacy during maintenance therapy see Table 10.

Further treatment of the patients other than venetoclax maintenance will be outside this clinical trial at the physicians' discretion.

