### Venetoclax

**Day 1 of venetoclax will define the study treatment start.** To mitigate the potential risk of TLS, venetoclax administration will start with a pre-specified dose ramp-up to reach the target dose level of 400 mg at day 4 (refer to Table 2).

Table 2: Venetoclax ramp up

Day	Venetoclax dose
1	50 mg
2	100 mg
3	200 mg
4 – 14 (10)*	400 mg

\* Venetoclax will be administered until day 14, only at dose level -1, venetoclax will be given until day 10.

Each dose of venetoclax should be taken with approximately 240 ml of water within 30 minutes after the completion of a meal, preferably breakfast. The dose should be administered at the same time each day. On days with planned cytarabine administration, venetoclax must be given prior to cytarabine and mitoxantrone. If a patient develops any lab changes suggestive of TLS within the first 24 hours after either first dose or during ramp up, venetoclax should be withheld until normalization of lab changes. Venetoclax will be administered in Phase I and II no longer than 10/14 days except during maintenance therapy.

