## 6.3 Assessment of safety

Regular safety assessment will ensure that patients have no or minimal study related risk. Safety evaluations will include results of physical examinations (including neurological disorders), vital signs (blood pressure, heart frequency, temperature), AEs, concomitant medications, and abnormal laboratory tests.

The following parameters will be used for safety assessment:

- Rate of early deaths (within 14 and 30 days) and induction deaths (until day 60 or until the beginning of next treatment – whichever occurs first)
- Incidence of serious infectious complications (Grades 3-5 CTCAE V5.0)

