#### Protocol-specific clarifications to this definition:

- Abnormal laboratory values should be evaluated by investigator for clinical significance and do not have to be documented as an AE if they are “not clinically significant”. They are to be documented in the database on the laboratory values eCRF form only.
- In order to monitor the safety of the trial participants throughout the trial, AEs need to be documented from first dose of venetoclax until 28 days after the last dose of venetoclax administered in the context of this trial.

- A pathological finding, improved or unchanged in comparison to baseline, does not constitute an AE.
- Symptoms of the disease under study should not be classified as AEs as long as they are within the normal day-to-day fluctuation. Worsening of the underlying disease (relapse or disease progression) or of other preexisting conditions will be recorded as an AE.

Adverse events are classified as either serious or non-serious:

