##### **8.1.5.3 Adverse events**

Adverse events occurring before the first administration of venetoclax will be assigned to the medical history and analyzed in that context.

Incidences of AEs will be reported with counts and percentage grouped by CTCAE toxicity grade, dose level, severity, relatedness to cytarabine, relatedness to venetoclax and overall. AEs leading to discontinuation, SAEs, and deaths will be listed as described for DLTs in section [8.1.5.2](#).

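### The main adverse event tables run to 28 days after the last venetoclax dose with no cut at the next anti-leukaemic therapy, so events of a later regimen can enter the tolerability rates

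*Protocol*

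**What the plan says.** **Collection.** Table 9 in section 6.1 records adverse events during induction "Continuously starting from day 1 until 28 days after last dose of venetoclax". Table 10 does the same in maintenance: "continuous till day 28 after last dose of IMP". The synopsis and sections 7.1.1, 7.2 and 7.3.1 give the same end point. None of them mentions the start of another anti-leukaemic treatment.

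**Dosing.** Section 5.4.1 states: "Venetoclax will be administered in Phase I and II no longer than 10/14 days except during maintenance therapy". Day 10 applies only to dose level -1.

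**Analysis.** Section 8.1.5.3 says "Incidences of AEs will be reported with counts and percentage grouped by CTCAE toxicity grade", and further by dose level, severity, relatedness to each of venetoclax and cytarabine, and overall. Section 8.2.7.2 carries this into phase II. Section 8.2.3.2 defines tolerability through all adverse events and their grade, and section 8.2.2.3 puts everyone exposed to venetoclax into the safety set.

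**Later treatment.** Section 3.4 says: "Further treatment of the patients other than venetoclax maintenance will be outside this clinical trial", and leaves it to the physician. Section 4.4.1 lists relapse and resistant disease among the reasons for leaving the study early.

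**A next-treatment cut elsewhere.** For induction deaths, section 6.3 counts to day 60 or "until the beginning of next treatment", taking the earlier of the two.

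**The concern.** A patient who moves to another intensive regimen before the window closes continues to contribute adverse events. Those events are counted in the overall and by-grade rates beside the events of V-MAC, and nothing in the table definition separates them by timing.

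Two uses of the data are exposed. One is tolerability, a named secondary endpoint. The other is the phase II check in section 3.3, where toxicities of grade 3 or higher are compared with published cohorts and an excess above 10% calls in the steering committee. Any distortion would tend to follow treatment failure, because patients with resistant disease have the most reason to change therapy early.

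**Working it through.** The plan states no figure on this point, so the check is day arithmetic.

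**Inputs**
- Last induction dose of venetoclax: day 14, or day 10 at dose level -1 (section 5.4.1).
- Follow-up for adverse events: 28 days after the last dose (Table 9).
- Early marrow: day 18-21. Remission assessment: day 28-45 (sections 3.4 and 6.4.2.2).
- Premature end-of-study visit in maintenance: 7 to 14 days after the last dose (Table 10, footnote f).
- Start of next therapy: not given, so assumed below.

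**Step 1: end of the window.** Last dose day + 28 gives 14 + 28 = day 42, and at level -1, 10 + 28 = day 38. If venetoclax is stopped earlier, the window closes correspondingly earlier.

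**Step 2: window days under another regimen.** Days = window end - start day + 1, counting the start day, and 0 if the start falls after the window.

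| Next therapy starts | Window to day 42 | Window to day 38 |
|---|---|---|
| Day 29 | 42 - 29 + 1 = 14 (33%) | 38 - 29 + 1 = 10 (26%) |
| Day 35 | 42 - 35 + 1 = 8 (19%) | 38 - 35 + 1 = 4 (11%) |
| Day 43 or later | 0 | 0 |

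Day 29 is the day after the earliest remission assessment.

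**Step 3: maintenance.** A patient seen for the premature end-of-study visit 7 to 14 days after the last dose still has 28 - 7 = 21 to 28 - 14 = 14 days of the window left.

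**Step 4: scale of the section 3.3 check.** This step assumes that the 10% excess means percentage points and that the denominator is 42. Then 0.10 x 42 = 4.2. Five patients whose only grade 3 or higher event of a given type arose under later therapy would add 5/42 = 11.9 points. This shows what would be enough; it is not a forecast.

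**Step 5: change in incidence.** If a share f of patients start new therapy in the window, a share q of those have the event because of it, and the background rate is b, the rise is f x q x (1 - b), assuming independence. None of the three inputs is in the protocol. For assumed ranges f = 10-30%, q = 30-60% and b = 20-60%, the rise runs from 0.1 x 0.3 x 0.4 = 1.2 points to 0.3 x 0.6 x 0.8 = 14.4 points. So wide a range from assumed inputs means that the effect cannot be derived from the document.

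**The case against.** **This belongs in the SAP.** A counting rule for treatment-emergent events is commonly set there, section 8.3 requires a SAP, and it is not shown. This carries weight and is one reason the point is minor. But the protocol itself fixes the window, the endpoint and the tables, and a SAP that follows them literally will pool the events. If the SAP already has the cut, the point is closed.

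**Routine further therapy comes later.** Section 5.6 places it after the end of study, and section 3.7 prints day 45 beside the remission assessment. This holds for the standard path. However, sections 3.4 and 6.4.2.2 make day 45 the latest date of a range that opens on day 28, and section 4.4.1 allows earlier exit, so overlap remains possible.

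**Section 6.3 is not a general rule.** Its cut belongs to a window that reaches day 60, and the 14- and 30-day deaths in the same sentence have none. This is correct: section 6.3 is a precedent within the protocol, not a rule that the adverse event analysis breaks.

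**Other tables limit the effect.** Relatedness to each drug is tabulated, and non-haematologic DLTs require relation to venetoclax (section 3.2). Both points stand. The relatedness tables separate part of the effect but do not change the overall and by-grade rates.

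**Stronger readings the documents do not support.**
- A reader might infer that half the window, in about 15 of 42 patients, falls under salvage. That needs a start on day 22 (42 - 22 + 1 = 21 days) in every non-responder (0.35 x 42 = 14.7). No treatment change is attached to the day 18-21 marrow, and section 8.2.4.2 also counts deaths, withdrawals and missing assessments as failures.
- A reader might see transplant conditioning as a main source. Planned conditioning from aplasia is excluded (section 4.2), and maintenance is meant for patients with no other post-remission option (section 3.4).
- A reader might conclude that start dates before the remission visit are missing, since footnote k of Table 9 records later AML therapies after the last study visit. But section 5.5 requires start and stop dates for all concomitant medication, and Tables 9 and 10 collect it over the same period as adverse events.

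**Conclusion.** The point holds as a minor one. Read literally, the protocol counts adverse events of a later anti-leukaemic regimen in the overall and by-grade incidences whenever that regimen starts inside the window. The overlap is 14 of 42 days for a start on day 29, 8 for day 35, and none after day 42. These figures rest on a last venetoclax dose on day 14 and on assumed start days. How many patients are affected, and by how much incidence would move, cannot be derived.

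The documents support saying that such events can be reported as V-MAC tolerability, not that they will be. Tolerability is descriptive (section 8.2.4), the section 3.3 excess leads only to a consultation, and the added events push that comparison towards caution.

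**What to change.** Leave adverse event and SAE collection and reporting unchanged. In sections 8.1.5.3 and 8.2.7.2, state that the main incidence tables count events with onset up to the earlier of two dates: 28 days after the last venetoclax dose, and the start of the next anti-leukaemic therapy, including conditioning. Tabulate events with later onset in the window separately, and keep the uncut table as supportive.

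No new data item is needed. Start dates inside the window come from the concomitant medication record (section 5.5, Tables 9 and 10), and later ones from footnote k of Table 9 and footnote g of Table 10.

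The cost is a sentence of wording and one extra table. Observation becomes shorter in patients who move on early, and some delayed V-MAC toxicity will appear in the second table. That is why the uncut table should be kept.

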	
 
• AML relapse treatment with any investigational or commercial drug within 14 days before enrolment. Hydroxyurea is allowed until enrolment to control peripheral WBC counts.
 
• Substance abuse, medical, psychological, or social conditions that may interfere with the subject’s cooperation with the requirements of the trial or evaluation of the study results
 
• Acute toxicities from any prior anti-leukemia therapy or from previous investigational drugs that have not resolved to Grade <2 per National Cancer Institute (NCI) Common Terminology Criteria for Adverse Events (CTCAE), Version 5.0
 
• History of active or chronic infectious hepatitis unless serology demonstrates clearance of infection (Occult or prior hepatitis B virus (HBV) infection (defined as negative hepatitis B surface antigen and positive total hepatitis B core antibody) may be included if HBV DNA is undetectable, provided that they are willing to undergo monthly DNA testing. Patients who have protective titers of hepatitis B surface antibody after vaccination or prior but cured hepatitis B are eligible. Patients positive for hepatitis C virus antibody are eligible provided PCR is negative for HCV RNA)
 
• History of clinically significant liver cirrhosis (e.g., Child-Pugh class B and C).
 
• Pregnant or breastfeeding patients
 
 
[Exact list of exclusion criteria is specified in section 4.2]
						

Trial drug
	
Investigational Medicine Products:
 
 
• venetoclax (ABT-199)
 
• cytarabine (Phase I/Escalation Phase only)
 
						

Treatment
	
Phase I: Escalation phase
 
The induction therapy starts with the first administration of venetoclax (day 1) and patients will be admitted to the hospital for at least the first week of study treatment.
 
Venetoclax will be administered in increasing doses until maximum daily dose of 400 mg. The treatment schedule will be as follows:
 
Venetoclax ramp up
 
  
 Day	Venetoclax daily dose	
   
 1	50 mg	
 
 2	100 mg	
  
	Day	Venetoclax daily dose	1	50 mg	2	100 mg
Day	Venetoclax daily dose						
1	50 mg						
2	100 mg						

3	200 mg
4 – 14 (10)	400 mg

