(Occult or prior hepatitis B virus (HBV) infection (defined as negative hepatitis B surface antigen and positive total hepatitis B core antibody) may be included if HBV DNA is undetectable, provided that they are willing to undergo monthly DNA testing. Patients who have protective titers of hepatitis B surface antibody after vaccination or prior but cured hepatitis B are eligible. Patients positive for hepatitis C virus antibody are eligible provided PCR is negative for HCV RNA.)
- History of clinically significant liver cirrhosis (e.g., Child-Pugh class B and C).
- Live-virus vaccines given within 28 days prior to the initiation of study treatment

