## 6.2 Study visits and diagnostic procedures

The table above lists only procedures which are specifically required for the evaluation of study aims and endpoints. Additional diagnostic and therapeutic procedures may be necessary according to clinical standard as defined in evidence-based AML treatment guidelines [NCCN guideline, Onkopedia-Leitlinie, Döhner et al 2010] and according to the investigator's clinical experience and expertise.

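### Table 9 footnote n ties the screening HBV DNA test to surface antibody, while section 4.2 makes it an entry condition for HBsAg-negative, core-antibody-positive patients

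*Protocol*

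**What the plan says.** Protocol section 4.2 excludes active or chronic infectious hepatitis unless serology shows clearance, and then sets out who may still enter. Occult or prior hepatitis B is defined as "negative hepatitis B surface antigen and positive total hepatitis B core antibody". Such patients are admitted if HBV DNA is undetectable, "provided that they are willing to undergo monthly DNA testing". The next sentence makes patients eligible who have protective surface-antibody titers after vaccination or after a cured infection, and it states no DNA condition. The synopsis repeats the rule: these patients "may be included if HBV DNA is undetectable, provided that they are willing to undergo monthly DNA testing".

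Section 6.1, Table 9, schedules virus diagnostics at screening only. Footnote n lists HBs-antigen and then "HBs-antibody (if positive HBs-antibody – HBV DNA required), anti-HBc, anti-HCV IgG (if positive anti-HCV IgG – HCV RNA required". It opens with a general reference to clinical standards.

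Table 10, the maintenance schedule, has no virus row. Section 6.6 has the eligibility criteria checked on day 1 before the first venetoclax dose, and a patient whose eligibility cannot be confirmed is a screening failure.

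**The concern.** The footnote exists to carry out the serology rule in 4.2 during screening, but its hepatitis B trigger sits on a different antibody. A site that orders tests from the schedule would send HBV DNA for a vaccinated patient. It would not be told to send it for a patient whose only positive marker is core antibody, and that is a patient whom 4.2 admits only with that result.

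What is at stake is confirmation of eligibility, and protection against hepatitis B reactivation under intensive chemotherapy plus venetoclax, in a small subgroup.

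**Working it through.** No figure in the plan has to be reproduced. The check sets the two rules side by side for each HBsAg-negative profile.

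| anti-HBc | anti-HBs | HBV DNA needed under 4.2 | HBV DNA prompted by footnote n |
|---|---|---|---|
| + | + | yes under the core-antibody definition; the sentence on cured infection could be read otherwise | yes |
| + | − | yes | **no** |
| − | + (vaccinated) | no | yes |
| − | − | no | no |

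**Row 2** is the real gap: the result decides eligibility, and the schedule does not ask for it.

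**Row 3** is a surplus test. Section 4.2 does not need it but does not bar it either, so nothing is contradicted and nobody is wrongly excluded.

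**Row 1** causes no problem in practice, because the test is prompted under either reading of 4.2.

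**Comparison within the same footnote.** For hepatitis C, a positive antibody leads to HCV RNA, which is the rule in 4.2. Only the hepatitis B trigger is on the wrong marker, which points to a drafting slip.

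**Number affected.** The plan foresees up to 18 patients in phase I and 42 in phase II, 18 + 42 = 60 before any phase I replacements. The Protocol gives no serology prevalence, so the number in row 2 is unknown and may be zero.

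**Monthly testing.** Section 4.2 names monthly HBV DNA testing but gives no duration, and neither table mentions it after screening. During V-MAC there is ample opportunity to draw the sample, since "blood count should be done 3x/week until hematologic recovery". In maintenance the visits after cycle 1 fall at "End of Cycle 2, 4, 6, 9" and at the end of cycle 12. With 28-day cycles these are days 56, 112, 168, 252 and 336. The gaps from the cycle 1 day 15 visit onward are therefore:

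- 56 − 15 = 41 days
- 112 − 56 = 56 days
- 168 − 112 = 56 days
- 252 − 168 = 84 days
- 336 − 252 = 84 days

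If monthly testing is meant to continue in maintenance, which is an assumption, some draws would fall between planned visits.

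**The case against.** There is a fair case that little can go wrong.

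- Footnote n refers to clinical standards and orders anti-HBc in every patient, so the investigator holds the result that activates 4.2 during screening.
- Section 4.2 is the governing eligibility rule and is available throughout the 14-day screening window. Table 9 has its own row for checking the criteria before the first dose.
- Section 6.2 limits the tables: "The table above lists only procedures which are specifically required for the evaluation of study aims and endpoints". It adds that further procedures may follow from clinical standard.

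Much of this stands, and it keeps the point small. It does not correct the trigger. A general reference to clinical standards does not override an explicit requirement placed on a named marker, and a statement about which procedures are listed cannot excuse a listed procedure with the wrong condition. The day 1 check comes after the window in which the test should have been ordered.

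A reader might infer three stronger things, none of which the Protocol supports:

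- **That ineligible patients will be treated.** The day 1 check, if followed, stops this. A late order or a delayed start is the likelier result.
- **That half of the four serology profiles are handled wrongly.** The test in vaccinated patients is an extra, so the gap is one profile.
- **That the missing monthly test contradicts 4.2.** Section 4.2 words it as willingness and fixes no duration, so a table without the entry conflicts with nothing. Section 6.2 is not a full answer here, because the tables already carry an eligibility test for a subgroup (Table 9, footnote h: "Women of childbearing potential must have a negative serum pregnancy test performed"). Even so, this is a missing detail and not an error.

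**Conclusion.** The concern holds for the trigger. Footnote n attaches the required HBV DNA test to anti-HBs and none to anti-HBc, while 4.2 and the synopsis make an undetectable result a condition of entry for HBsAg-negative, anti-HBc-positive patients. One serology profile, isolated anti-HBc positivity, is left without a prompt in the schedule.

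The severity is minor. The conclusion rests on the wording alone and needs no assumption about prevalence, although how often it would matter cannot be judged from the Protocol. It bears on eligibility and safety procedures. The MTD, the CR/CRi endpoint, the sample size and the error rates are unaffected. The monthly test is an accompanying clarification only.

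**What to change.** In Table 9, footnote n, attach the DNA requirement to the core antibody: if anti-HBc positive and HBsAg negative, HBV DNA required. Dropping the anti-HBs trigger is optional; it would save an unneeded test in vaccinated patients.

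As a clarification, add to Tables 9 and 10 a conditional cross-reference to the monthly HBV DNA test in 4.2, and state there how long it continues.

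The trigger correction is one line and adds no test that 4.2 does not already require. The cross-reference costs nothing during V-MAC, where blood is drawn often. If testing is to continue in maintenance, some monthly samples would need a draw between planned visits, on site or elsewhere, for the affected patients only.
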